1. SYNOPSIS

Name of Sponsor/Company: LB Pharmaceuticals, Inc.

Name of Investigational Product: LB-102

Name of Active Ingredient: *N*-methyl amisulpride

Protocol Number: LB-102-001

Title of Study: A Randomized, Double-Blinded, Placebo-Controlled, Single and Multiple Ascending Dose Study to Evaluate the Safety, Tolerability, and Pharmacokinetics of LB-102 Administered Orally to Healthy Subjects

Estimated Number of Study Center(s): Single Center

Phase of Development: 1

Objectives:

The Primary Objectives:

Part A (SAD)

• To evaluate the safety and the tolerability of a single oral dose of LB-102 compared to placebo

Part B (MAD)

• To evaluate the safety and the tolerability of multiple oral doses of LB-102 compared to placebo

The Secondary Objectives:

Part A (SAD)

• To evaluate the pharmacokinetics (PK) of a single dose of LB-102

Part B (MAD)

• To evaluate the PK of multiple oral doses of LB-102

Study Design: This is a Phase 1, randomized, double-blind, placebo-controlled study designed to evaluate the safety, tolerability, and PK of LB-102 in healthy subjects. The study will consist of two parts: Part A – Single Ascending Dose and Part B – Multiple Ascending Doses. There will be 5 cohorts in Part A and 3 Cohorts in Part B of this study. Each cohort consists of 8 subjects, with 6 subjects assigned to LB-102 treatment and 2 subjects assigned to placebo treatment.

In Parts A and B, eligible subjects will be randomized on Day 1 (pre-dose) to placebo (n=2) or LB-102 (n=6) treatment. Eligible subjects will receive 1 dose on Day 1 (Part A) or 13 doses on Days 1-7 (Part B) of placebo or LB-102. In Cohort 1 (Part A), dosing of the first 2 subjects (1 active and 1 placebo) will commence at least 24 hours prior to the remaining 6 subjects. Dosing of the remaining subjects in the cohort may proceed if no safety issues are identified for the first 2 subjects. Blood samples for PK and safety assessments will be collected at nominal timepoints described below. Subjects will be discharged on Day 3 (Part A) or Day 9 (Part B)

and return for a Follow-up Visit (Day 8 or Day 15, respectively) for safety review. For Cohort 5 (Part A), subjects will return for an additional Follow-Up Visit.

A Safety Review Committee (SRC) will be assembled to review the blinded available study results for a cohort and agree whether the safety profile is sufficiently acceptable to support proceeding with the evaluation of the next higher dose level. The SRC will be comprised of the Investigator, Medical Monitor, and a Sponsor Representative (voting members). Other non-voting consultants, including to but not limited to, PK or medical expert, statistician, etc. may support the SRC on an as needed basis. Blinded data to be reviewed at the end of each cohort includes, but is not limited to adverse events, physical examinations, vital signs, 12-lead ECGs, clinical laboratory safety tests, and concomitant medications/procedures. Blinded PK analysis will occur at the end of each Cohort (Cohorts 1-5) for the SAD study and after the 1st cohort for the MAD study.

	Part A		
Cohort	Treatment		
1 (n=8) ^a	LB-102 50 mg (n=6) or Matching Placebo (n=2) QD x 1 day		
2 (n=8) ^b	LB-102 10 mg (n=6) or Matching Placebo (n=2) QD x 1 day		
3 (n=8) ^b	LB-102 100 mg (n=6) or Matching Placebo (n=2) QD x 1 day		
4 (n=8) ^b	LB-102 200 mg (n=6) or Matching Placebo (n=2) QD x 1 day		
5 (n=8) ^b	LB-102 150 mg (n=6) or Matching Placebo (n=2) QD x 1 day		
	Part B		
6 (n=8)	LB-102 (n=6) 50 mg BID (100 mg/day) x 6 days (Days 1-6) and QD x 1 day (Day 7) or Matching Placebo (n=2) BID x 6 days (Days 1-6) and QD x 1 day (Day 7)		
7 (n=8)	LB-102 (n=6) Y* mg BID x 6 days (Days 1-6) and QD x 1 day (Day 7) or Matching Placebo (n=2) BID x 6 days (Days 1-6) and QD x 1 day (Day 7)		
8 (n=8)	LB-102 (n=6) Y* mg BID x 6 days (Days 1-6) and QD x 1 day (Day 7) or Matching Placebo (n=2) BID x 6 days (Days 1-6) and QD x 1 day (Day 7)		

a – In Cohort 1 (Part A), dosing of the first 2 subjects (1 active and 1 placebo) will commence at least 24 hours prior to the remaining 6 subjects.

b – For Cohorts 2-5, the doses may be reduced based on the PK results of Cohort 1 (Refer to Section 5.1).

 Y^* - Dose will be determined by the SRC depending on the safety profile and clinical observations of the previous Cohort.

QD = Once daily; BID = Twice daily

Number of Subjects (Planned): A total of 64 subjects will be enrolled with 8 subjects being randomized for each of 8 cohorts (exclusive of possible replacements). Subjects will be considered enrolled at the point they are randomized to treatment.

Diagnosis and Main Criteria for Eligibility:

Inclusion Criteria:

A subject will be eligible for inclusion in the study if he or she meets the following criteria:

- 1. Competent to provide informed consent.
- 2. Voluntarily provide informed consent and Health Insurance Portability and Accounting Act (HIPAA) Authorization in accordance with local regulations and governing Institutional Review Board (IRB) requirements prior to any procedures or evaluations performed specifically for the sole purpose of the study.
- 3. Healthy adult male and female subjects between 18 to 55 years of age inclusive at the screening visit.
- 4. Body Mass Index (BMI) \geq 18 and \leq 30 kg/m² at screening visit.
- 5. Subjects must be in good general health as determined by medical history and physical examination with no clinically significant medical findings and no history of significant medical disease (e.g., cardiovascular, pulmonary, renal, etc.) or acute condition with the past 30 days.
- 6. Have normal clinical laboratory test results and ECG, which are not considered to be clinically significant by the Investigator.
- 7. Females participating in the study:
 - a. Either must be of non-childbearing potential [surgically sterilized: hysterectomy, bilateral tubal ligation, salpingectomy, and/or bilateral oophorectomy at least 26 weeks before the Screening Visit] or postmenopausal. Menopause is defined as being amenorrhoeic for at least 2 years with plasma follicle-stimulating hormone (FSH) levels in the post-menopausal range at screening, based on the central laboratory's ranges; OR
 - b. Females of child-bearing potential must have a negative pregnancy test and be not breastfeeding at Screening and use either abstinence or an accepted contraception method during the treatment period and for an additional period of 30 days after the end of investigational treatment. For this study, accepted contraception methods include:
 - i. condom plus spermicide
 - ii. condom plus diaphragm
 - iii. condom plus cervical cap or female condom
 - iv. hormonal contraceptives
 - v. intrauterine device

- vi. partner vasectomy and a use of barrier contraception methods
- 8. If male, subject must be surgically sterile or practicing at least 1 of the following methods of contraception, from initial study drug administration through 90 days after administration of the last dose of study drug:
 - a. Have had a vasectomy (at least 6 months earlier);
 - b. Use of a double-barrier contraception method, defined as male use of a condom and female use of a barrier method (e.g., contraceptive sponge, spermicidal jelly or cream with or without a diaphragm);
 - c. Partner use of hormonal contraceptives (oral, parenteral, vaginal, or transdermal) for at least 3 months prior to study drug administration;
 - d. Partner use of an intrauterine device;
 - e. Complete abstinence from sexual intercourse;
 - f. Male subjects not practicing complete abstinence must use a condom as a required form of birth control (in addition to at least 1 of the other methods listed above, if desired) in order to protect partners of male participants from exposure to study drug.
- 9. If male, subject must agree to abstain from sperm donation through 90 days after administration of the last dose of investigational drug.

Exclusion Criteria:

A subject will be excluded from the study if he or she meets the following criteria:

- 1. Are pregnant or lactating.
- 2. Have a history or presence of significant cardiovascular, respiratory, hepatic, renal, gastrointestinal, endocrine, or neurological disorders which, in the opinion of the Investigator, increases the risk of the study drug or may confound the interpretation of study measures.
- 3. Clinically significant abnormal findings on physical examination or vital signs.
- 4. History or presence of psychiatric or neurological disease or condition.
- 5. History of seizures.
- 6. Subject with any history or current evidence of suicidal behavior.
- 7. Unwilling to complete any planned study assessments, including the Columbia-Suicide Severity Rating Scale (C-SSRS).
- 8. Recent history of alcohol or drug abuse (within the last two years).
- 9. Any use of tobacco or tobacco-containing products (cigarettes, pipes, etc.) within one month prior to Screening.
- 10. Have a history of blood donation in excess of 500 mL of blood within 30 days prior to Screening.

- 11. Have received treatment with an investigational drug or device within 60 days prior to Screening.
- 12. Use of any prescription or over the counter medication, herbal medications, vitamins, or supplements within 14 days prior to study drug administration.
- 13. Have a positive test for Human Immunodeficiency Virus (HIV) antibodies 1 and 2, Hepatitis B Surface Antigen (HBsAg) or Hepatitis C Virus (HCV) antibody.
- 14. Any subject who is known to be allergic to the study drug or any components of the study drug.
- 15. The subject has a fasting blood glucose \geq 126 mg/dL or hemoglobin A1c (HbA1c) \geq 6.5% at Screening.
- 16. The subject has a history of QT prolongation or dysrhythmia or a family history of prolonged QT interval or sudden death.
- 17. Clinically significant abnormal finding on ECG and/or evidence of any of the following cardiac conduction abnormalities at Screening (ECG will be measured once in Part A for Cohorts 1-4. ECG will be measured in triplicate in Part A for Cohort 5 and Part B, mean values will be used for the following criteria):
 - a. Heart rate < 40 bpm and > 100 bpm (based on the ECG reading)
 - b. QTcF interval > 450 msec for males and females
 - c. PR interval \geq 200 msec
 - d. Intraventricular conduction delay with QRS duration > 120 msec
 - e. Evidence of second- or third-degree atrioventricular block (AVB)
 - f. Electrocardiographic evidence of complete left bundle branch block (LBBB), complete right bundle branch block (RBBB), or incomplete LBBB

Test Product, Dose, and Mode of Administration:

N-methyl amisulpride (LB-102) Powder in Capsule in dosage strengths of 25 mg, 50 mg, 75 mg, and 100 mg, Oral administration

Reference Therapy, Dosage and Mode of Administration: Matching placebo capsules to be taken orally as described above.

Duration of Treatment: Part A: 1 day; Part B: 7 days.

Endpoints:

Safety:

The following schedule represents the ideal study schedule. It should be used as guidance for study conduct. In the event there are delays at any visit days that may affect the dates of any subsequent visit, the planned days may vary. The following will be monitored to assess safety:

- AEs
- Hematology, chemistry, urinalysis at:
 - o Part A: Screening, Check-in (Day 0), Day 2, and at Follow-up (Day 8).

- o Part B: Screening, Check-in (Day 0), Day 4 prior to first dose, Day 8, and at Follow-up (Day 15).
- Prolactin at:
 - o Part A: Screening, Day 3, Day 8, and Day 15 (For Cohort 5, Part A only).
 - o Part B: Screening, Day 4, Day 9, and Day 15.
- ECG
 - o Part A: Screening, Check-in, Day 1 at pre-dose and at 1, 2, 3, 4, 5, 6, 8 and 24 (Day 2) hours (±30 min) post-dose on Day 1. ECG will be measured once at each time point for Cohorts 1-4 and in triplicate for Cohort 5.
 - o Part B: Screening, Check-in, Day 1 prior to the first dose and at 1, 2, 3, 4, 5, 6, and 8 hours (±30 min) post first dose on Day 1 prior to first dose on Days 2-7, and Day 8 (24 hours post-dose Day 7; ±30 min). ECG will be measured in triplicate at each time point.
- Physical examination
 - o Part A: Screening, Check-in, Day 2, and Follow-up (Day 8).
 - o Part B: Screening, Check-in, Days 2, 4, and 8, and Follow-up (Day 15).
- Vital signs (heart rate, respiratory rate, temperature, and blood pressure)
 - o Part A: Screening, Check-in, Day 1 at pre-dose and at 0.5, 1, 1.5, 2, 4, 6, 8, 12, 24 (Day 2), and 48 hours (Day 3) post-dose (±30 min), and at Follow-up (Day 8).
 - o Part B: Screening, Check-in, Day 1 prior to first dose and at 0.5, 1, 1.5, 2, 4, 6, 8 and 12 hours (±30 min) post first dose on Day 1, prior to first dose and 2 hours (±30 min) post first dose on Days 2-7, 24 and 48 hours (±30 min) post Day 7 dose (Day 8 and 9), and at Follow-up.
- C-SSRS
 - o Part A: Screening, Day 3
 - o Part B: Screening, Day 4, and Day 8.

Pharmacokinetics:

Plasma PK samples will be obtained at the following nominal time points:

- Part A
 - O Day 1: pre-dose, 15, 30, and 45 minutes (±5 minutes), and 1, 1.5, 2, 3, 4, 6, 8, 12, and 16 hours (±15 min) post-dose.
 - o Days 2-3: 24, 32, and 48 hours (±15 min) post Day 1 dose.
 - o Days 8 and 15 (For Cohort 5, Part A only).
- Part B
 - O Day 1: prior to the first dose, 15, 30, and 45 minutes (±5 minutes), and 1, 1.5, 2, 3, 4, 6, 8, 12, and 16 hours (±15 min) post first dose.
 - o Days 2-6: prior to first dose.
 - O Day 7: pre-dose, 15, 30, and 45 minutes (±5 minutes), and 1, 1.5, 2, 3, 4, 6, 8, 12, and 16 hours (±15 min) post dose.
 - o Days 8-9: 24, 32, and 48 hours (±15 min) post Day 7 dose.

Statistical Analysis

Safety: Statistical methods will be primarily descriptive in nature. No formal statistical comparisons of dose levels will be made. Categorical variables will be summarized using numbers and percentages. Continuous variables will be summarized by total number (N), mean, standard deviation, median, minimum, and maximum. Each cohort will be evaluated separately

for safety. All placebo subjects from the different cohorts will be combined into a single group for summary purposes.

A formal statistical analysis plan (SAP) will be developed and finalized prior to unblinding the data. This plan will define populations for analysis, outline all data handling conventions, and specify all statistical methods to be used for analysis of the data. A separate PK analysis plan will be created.

Safety data, including vital signs, ECGs, laboratory test results, physical examinations, and AEs, will be summarized by dose and assessment time points, as appropriate. Change from baseline will be included in summary tables for laboratory, ECG and vital sign parameters.

Pharmacokinetics: Plasma concentrations of LB-102 and amisulpride will be measured during the study and PK parameters derived using non-compartmental and/or compartmental methods as appropriate. The following PK parameters (as appropriate) will be calculated: AUC_{0-t}, AUC₀₋₂₄, AUC_{0-inf}, AUC_{%extrap}, CL/F, C_{max}, T_{max}, λ_z, and t_{1/2}.

No value for λ_z , AUC_{0-inf}, CL/F, or $t_{1/2}$ will be reported for cases that do not exhibit a terminal log-linear phase in the concentration versus time profile.

No PK parameters will be calculated for subjects with detectable concentrations for 2 or fewer time points.

Individual and mean plasma concentration time curves (both linear and log-linear) will be included in the final report.

PK parameters of LB-102 and amisulpride will be summarized by cohort using descriptive statistics (sample size, arithmetic means, geometric means, standard deviation, % coefficient of variation, minimum, median, and maximum). Figures will be created to display mean and individual subject LB-102 and amisulpride concentration time curves in plasma on both a linear and logarithmic scale. Dose proportionality will be assessed using a linear regression, or other acceptable approach.

Sample Size Determination:

The sample size for the study is based on clinical rather than statistical rationale. No formal sample size calculations were made. Cohorts of 8 subjects (6 active, 2 placebo) are sufficient to characterize the safety, tolerability, and PK profile of LB-102.

Table 1: Schedule of Events for Part A

	Screening	Check-In		Treatment Evalu	ation	Follow-Up Visits
Visit	1	2		3		4 and 5
Days	Days -28 to -1	Day 0	Day 1	Day 2	Day 3	Days 8 and 159
Informed Consent	X					
Inclusion/Exclusion Criteria	X	X				
Medical History	X	X				
Demographics	X					
Randomization			X			
Height, Weight, BMI ¹	X					X (Day 8 Only)
Physical Examination	X	X		X		X (Day 8 Only)
Vital Signs ²	X	X	X	X	X	X (Day 8 Only)
Laboratory Tests	X	X		X		X (Day 8 Only)
Serum HbA1c	X					
Serum Prolactin	X				X	X
HIV, HBsAg, and HCV Labs	X					
12-Lead ECG ³	X	X	X	X		
C-SSRS	X				X	
Urine Drug Screening	X	X				
Alcohol Breathalyzer	X	X				
Pregnancy Test ⁴	X	X				X (Day 8 Only)
FSH ⁵	X					
Plasma PK ⁶			X	X	X	X
Dose Subjects ⁷			X			
Concomitant Medication ⁸	X	X	X	X	X	X
Adverse Event Assessment ⁸		X	X	X	X	X

Notes to the Schedule of Events for Part A:

BMI = Body Mass Index; C-SSRS = Columbia-Suicide Severity Rating Scale; ECG = Electrocardiogram; FSH = Follicle-Stimulating Hormone; HbA1c = Hemoglobin A1c; HBsAg = Hepatitis B Surface Antigen; HCV = Hepatitis C Virus; HIV = Human Immunodeficiency Virus; PK = Pharmacokinetic

¹ Only Weight will be recorded at Follow-Up, height and BMI will not.

² Vital Signs will be measured at Screening, Check-in, Day 1 at pre-dose and 0.5, 1, 1.5, 2, 4, 6, 8, 12, 24, and 48 (±30 min) hours post-dose, and at Follow-up (Day 8).

³ ECG will be measured at Screening, Check-in, Day 1 at pre-dose and 1, 2, 3, 4, 5, 6, 8, and 24 (±30 min) hours post-dose. ECG will be measured once at each time point for Cohorts 1-4 and in triplicate (approximately 1 min apart) for Cohort 5.

⁴ Serum pregnancy test at Screening and Urine pregnancy test at Day 0 and Day 8 for all females of childbearing potential.

⁵ FSH test for postmenopausal women.

⁶ Plasma PK samples will be collected on Day 1 at pre-dose, 15, 30, and 45 minutes (±5 minutes), and 1, 1.5, 2, 3, 4, 6, 8, 12, 16, 24, 32, and 48 hours (±15 min) post-dose, and Days 8 and 15.

⁷ Subjects are required to fast for approximately 12 hours prior to Day 1 dosing.

⁸ Concomitant Medication and Adverse Event Assessment will be recorded once per day on the days indicated.

⁹ Day 15 Follow-Up Visit is scheduled for Cohort 5, Part A only.

Table 2: Schedule of Events for Part B

	Screening	Check-In		Treatment Evalua	tion	Follow-Up Visi
Visit	1	2		3		4
Days	Days -28 to -1	Day 0	Day 1	Days 2-7	Days 8-9	Day 15
Informed Consent	X					
Inclusion/Exclusion Criteria	X	X				
Medical History	X	X				
Demographics	X					
Randomization			X			
Height, Weight, BMI ¹	X					X
Physical Examination	X	X		X (Days 2, 4 only)	X (Day 8 only)	X
Vital Signs ²	X	X	X	X	X	X
Laboratory Tests	X	X		X (Day 4 only)	X (Day 8 only)	X
Serum HbA1c	X					
Serum Prolactin	X			X (Day 4 only)	X (Day 9 only)	X
HIV, HBsAg, and HCV Labs	X					
12-Lead ECG ³	X	X	X	X	X (Day 8 only)	
C-SSRS	X			X (Day 4 only)	X (Day 8 only)	
Urine Drug Screening	X	X				
Alcohol Breathalyzer	X	X				
Pregnancy ⁴	X	X				X
FSH ⁵	X					
Plasma PK ⁶			X	X	X	
Dose Subjects ⁷			X	X		
Concomitant Medication ⁸	X	X	X	X	X	X
Adverse Event Assessment ⁸		X	X	X	X	X

Notes to the Schedule of Events for Part B:

BMI = Body Mass Index; C-SSRS = Columbia-Suicide Severity Rating Scale; ECG = Electrocardiogram; FSH = Follicle-Stimulating Hormone; HbA1c = Hemoglobin A1c; HBsAg = Hepatitis B Surface Antigen; HCV = Hepatitis C Virus; HIV = Human Immunodeficiency Virus; PK = Pharmacokinetic

¹ Only Weight will be recorded at Follow-up, height and BMI will not.

² Vital Signs will be measured at Screening, Check-in, Day 1 prior to the first dose and at 0.5, 1, 1.5, 2, 4, 6, 8, and 12 (±30 min) hours post first dose, prior to the first dose and 2 hours (±30 min) post first dose on Days 2-7, 24 and 48 hours (±30 min) post Day 7 dose, and at Follow-up.

³ ECG will be measured in triplicate at Screening, Check-in, Day 1 prior to the first dose and 1, 2, 3, 4, 5, 6, and 8 hours (±30 min) post first dose, prior to first dose on Days 2-7, and Day 8 (24 hours (±30 min) post Day 7 dose).

⁴ Serum pregnancy test at screening and Urine pregnancy test at Day 0 and Day 15 for all females of childbearing potential.

⁵ FSH test for postmenopausal women.

⁶ Plasma PK samples will be collected on Day 1 prior to the first dose and 15, 30, and 45 minutes (±5 minutes), and 1, 1.5, 2, 3, 4, 6, 8, 12 and 16 hours (±15 min) post first dose, Days 2-6: prior to first dose, Day 7 prior to the first dose and 15, 30, and 45 minutes (±5 minutes), and 1, 1.5, 2, 3, 4, 6, 8, 12, 16, 24, 32, and 48 hours (±15 min) post first dose.

⁷Subjects are required to fast for approximately 12 hours prior to the first Day 1 dose. On Days 1-6, subjects will receive 2 doses per day (8 AM and 8 PM \pm 1 hour) separated by approximately 12 hours. On Day 7, subjects will receive 1 dose (8 AM \pm 1 hour).

⁸ Concomitant Medication and Adverse Event Assessment will be recorded once per day on the days indicated.

TABLE OF CONTENTS

1.	SY	NOPSIS	5
2.	LIS	ST OF ABBREVIATIONS AND DEFINITIONS OF TERMS	20
3.	IN'	TRODUCTION	22
	3.1	Background and Rationale	22
	3.2	Description	23
	3.3	Nonclinical Pharmacology	24
	3.3	3.1 Pharmacodynamics	24
	3.4	Clinical Experience and Pharmacokinetics	24
4.	OF	BJECTIVES	26
5.	ST	UDY DESIGN	27
	5.1	Overall Study Design and Plan	27
	5.2	Discussion of Study Design	29
	5.3	Study Sites	29
	5.4	Selection of Study Population	29

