In Part A, eligible subjects, in 5 cohorts, will be randomized on Day 1 (pre-dose) to placebo (n=2) or LB-102 (n=6) treatment for a total of 40 subjects. Four (4) visits will occur as follows: Screening (Visit 1, Days -28 to -1), Check-in (Visit 2, Day 0), Treatment Evaluation (Visit 3, Days 1-3), and Follow-up (Visit 4, Day 8 and Visit 5, Day 15 [for Cohort 5, Part A only]). The study procedures for these visits are presented in detail in Table 1. Dosage of LB-102 will begin at 50 mg/day and subsequent groups will administered 10, 100, 200, and 150 mg/day, respectively. In Cohort 1 (Part A), dosing of the first 2 subjects (1 active and 1 placebo) will commence at least 24 hours prior to the remaining 6 subjects. Dosing of the remaining subjects in the cohort may proceed if no safety issues are identified for the first 2 subjects. On Day 1, following a 12-hour overnight fast, subjects will receive 1 oral dose of placebo or LB-102 at 8 AM (±1 hour). For each cohort, blood samples for PK will be collected on Day 1 at pre-dose and at 15, 30, and 45 minutes (±5 min), and 1, 1.5, 2, 3, 4, 6, 8, 12, 16, 24, 32, and 48 hours (±15 min) post-dose, and Day 8 and Day 15. Vital signs will be recorded for each subject at Screening, Check-in, Day 1 at pre-dose and at 0.5, 1, 1.5, 2, 4, 6, 8, 12, 24, and 48 hours (±30 min) post-dose, and at the Follow-up visit (Day 8). 12-lead ECG will be done on at Screening, Check-in, Day 1 at pre-dose and 1, 2, 3, 4, 5, 6, 8 and 24 hours (±30 min) post-dose. ECG will be measured once at each time point for Cohorts 1-4 and in triplicate for Cohort 5. Clinical labs (hematology, chemistry, urinalysis) will be assessed at Screening, Check-in, Day 2, and Follow-Up. Hemoglobin A1c (HbA1c) will be measured in serum at Screening, Prolactin will be measured in serum at Screening, Day 3, Day 8, and Day 15, C-SSRS will be assessed at Screening and Day 3. Subjects will remain in the clinic from Check-in to Discharge on Day 3 for additional safety assessment and then return for a Follow-up Visit on Day 8. Subsequent groups will follow the same study procedures.

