8.5.7.2 Eliciting and Documenting Adverse Events

The Investigator is responsible for ensuring that all AEs and SAEs are recorded in the CRF and reported to the Medical Monitor. Adverse events will be collected from Check-in (Day 0) through the Day 8 (Cohorts 1-4, Part A; End of Study), or 15 (Cohort 5, Part A or Cohorts 6-8, Part B, respectively; End of Study), or Early Discontinuation Visit.

At each visit, subjects will be asked for any medically related changes in their well-being. They will also be asked if they have had any accidents, used any new medications, or changed concomitant medication regimens (both prescription and over-the-counter medications). In addition to subject observations, AEs will be documented from any data collected on the AE page of the CRF (e.g., clinical laboratory values, physical examination findings, and ECG changes) or other documents that are relevant to subject safety.

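### One placebo group is formed across the single-dose and multiple-dose parts although AE follow-up ends at Day 8 for some cohorts and Day 15 for others, which shifts cumulative AE comparisons

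*Protocol*

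**What the plan says.** The Synopsis, under Statistical Analysis (Safety), has the rule: "All placebo subjects from the different cohorts will be combined into a single group for summary purposes". Cohorts are numbered 1 to 8 in one series over both parts, and nothing limits the rule to cohorts of the same part.

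The design behind it is:

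- Size: "There will be 5 cohorts in Part A and 3 Cohorts in Part B of this study", and "Each cohort consists of 8 subjects, with 6 subjects assigned to LB-102 treatment and 2 subjects assigned to placebo treatment".
- Dosing: "Eligible subjects will receive 1 dose on Day 1 (Part A) or 13 doses on Days 1-7 (Part B) of placebo or LB-102".
- Confinement: to Day 3 in Part A and to Day 9 in Part B (Synopsis, Study Design).
- AE window (Section 8.5.7.2): "Adverse events will be collected from Check-in (Day 0) through the Day 8 (Cohorts 1-4, Part A; End of Study), or 15" for Cohort 5 and for Part B.

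Section 4 sets two primary objectives, one per part, each a comparison with placebo. Section 6.1 randomizes new participants 3:1 within each cohort. Section 9.3.3 summarizes AE incidence by treatment. It mentions neither an adjustment for length of observation nor a split by part.

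**The concern.** The proportion of subjects with at least one AE grows with the time they are watched. Half of the merged placebo group is watched to Day 8 and half to Day 15, while each active cohort has only one of these windows. The merged rate is therefore expected to fit neither. It is too high as a comparator for a cohort followed to Day 8 and too low for one followed to Day 15, even if the drug does nothing.

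The merged column is also the randomized control of neither part. These descriptive tables are what the plan offers in answer to the primary objectives, so a shift with a predictable direction in them is worth removing if that is cheap.

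**Working it through.** **1. Counts.** The plan states: "A total of 64 subjects will be enrolled with 8 subjects being randomized for each of 8 cohorts". This reproduces: 8 × 8 = 64, with 5 × 8 = 40 in Part A and 3 × 8 = 24 in Part B. Placebo: 5 × 2 = 10 in Part A, 3 × 2 = 6 in Part B, 16 in all.

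**2. Placebo subjects by AE window.** To Day 8: Cohorts 1-4, 4 × 2 = 8. To Day 15: Cohort 5 (2) plus Part B (6) = 8. Mean planned follow-up from Day 1 is (8 × 8 + 2 × 15)/10 = 9.4 days in Part A, 15 days in Part B and (94 + 90)/16 = 11.5 days merged.

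**3. Direction.** Let a be the placebo AE risk by Day 8 and b the risk by Day 15. The merged rate is P = (8a + 8b)/16, the midpoint. Hence P − a = (b − a)/2 and P − b = −(b − a)/2. Cumulative incidence cannot fall with time, so b ≥ a and the signs are fixed under equal daily risk. An inert drug looks better than placebo in Cohorts 1-4 and worse in Cohort 5 and Cohorts 6-8.

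**4. Size.** The protocol gives no placebo AE rate; Appendix 1 describes Part A events but no such rate. Assumption: a constant daily hazard h, the same in all subjects, and no drug effect, so risk = 1 − exp(−h × days). Differences are taken before rounding.

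| h per day | a (Day 8) | b (Day 15) | P (merged) | Shift, either way | SE of P |
|---|---|---|---|---|---|
| 1% | 7.7% | 13.9% | 10.8% | 3.1 points | 7.7 points |
| 3% | 21.3% | 36.2% | 28.8% | 7.4 points | 11.2 points |
| 5% | 33.0% | 52.8% | 42.9% | 9.9 points | 12.1 points |

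SE of P = √[8a(1 − a) + 8b(1 − b)]/16. The shift is below this SE in every row, before the noise of a six-subject active cohort is added. Counting Day 0 as well (9 and 16 days) gives 3.1, 7.2 and 9.4 points.

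**5. Is pooling within each part enough?** No. Part A placebo would still mix 8 subjects followed to Day 8 with 2 followed to Day 15. At 3% per day its rate is (8 × 21.3% + 2 × 36.2%)/10 = 24.3%. Cohort 5's false excess then rises from 7.4 points to 36.2 − 24.3 = 11.9 points. With the Part A table cut at Day 8 for all cohorts, active and placebo, the expected difference under an inert drug is zero. Part B is followed to Day 15 in both arms, so its own placebo group removes the shift there.

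**6. Cost in precision.** The one-sided 95% upper bound with zero events is 1 − 0.05^(1/n): 17% for n = 16, 26% for n = 10, 39% for n = 6.

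**The case against.** The best argument for merging is that it trades a little bias for a larger denominator. At 3% per day the root-mean-square error of the Part B placebo rate is √(11.2² + 7.4²) = 13.4 points merged, against √(0.362 × 0.638/6) = 19.6 points from six subjects alone. At 1% it is 8.3 against 14.1 and at 5% about 15.6 against 20.4. For Cohorts 1-4 the two choices are nearly equal (13.4 merged against 13.0 for n = 10 cut at Day 8, at 3%). This stands, and it is the reason to keep an all-placebo column. It does not justify having only that column, since showing placebo by part as well loses nothing and restores each part's randomized control.

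The context also limits the point. The methods are descriptive, and the sentence before the pooling rule has each cohort evaluated separately. Laboratory, ECG and vital-sign data are summarized by time point, where length of follow-up matters little. The pooling sentence stands only in the Synopsis, and the SAP, which is not at hand, may show placebo by part. All this narrows the point to cumulative AE incidence. It does not remove a rule that the protocol states.

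A reader might infer four stronger things that the protocol does not support.

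- **That Part A and Part B are shifted in opposite directions throughout.** Cohort 5 is in Part A but is followed to Day 15, so on the same model it is shifted like Part B. For follow-up the divide is Cohorts 1-4 against Cohorts 5-8.
- **That 150 mg will look worse than 100 or 200 mg only because it is watched longer.** The gap b − a at 3% per day is 14.9 points, but it rests on an assumed rate and is less than one subject in six (16.7 points).
- **That ECG comparisons are biased too**, because "ECG will be measured once at each time point for Cohorts 1-4 and in triplicate for Cohort 5" and Part B is in triplicate. Replication changes the precision of a reading, not its expected mean, and the protocol announces no QTcF outlier table. No bias is shown.
- **That escalation or error rates are affected.** Section 8.5.3 acts on individual events in the cohort, with treatment checked for the subjects concerned, and no formal comparison of dose levels is planned.

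**Conclusion.** The point holds for cumulative AE incidence. As written, the placebo group mixes single-dose with 13-dose subjects and 8-day with 15-day follow-up, while each part's primary objective calls for a comparison with placebo of its own. The direction follows from the follow-up windows if daily risk is otherwise equal: in favour of the drug in Cohorts 1-4, against it in Cohort 5 and Part B.

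The size, about 3 to 10 points either way, depends wholly on an assumed constant 1% to 5% per day. That model also treats days in the unit and days after discharge alike. The shift is less than the sampling error, so it would seldom change the reading of a single table by itself. It is a systematic error in a descriptive comparison, worth correcting because correction is cheap, and not a defect that undermines the trial.

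**What to change.** - In the Synopsis, replace the single-group rule with placebo by part: Part A placebo (n = 10) and Part B placebo (n = 6), each the main comparator for the active cohorts of its own part. Repeat this in Section 9.3.3.
- Keep the all-placebo column (n = 16) as a labelled supplement.
- In Part A, cut the main AE incidence table at Day 8 for every cohort, active and placebo, and list Cohort 5 events of Days 9-15 separately. This step must go with the first; without it, pooling within Part A increases Cohort 5's false excess.

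The change needs no new data and no change in conduct, only wording and table work. Its downside is the smaller placebo denominators, with the wider zero-event bounds shown in the working (26% and 39% against 17%).
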